Median survival and time to progression were 21 months and 10 months among patients with less than 25% liver volume involvement, 7 months and 4.5 months among patients with 26-50% liver volume involvement, and 5 months and 3 months among patients with 51-75% liver volume involvement, respectively. According to RECIST criteria, 12 of the 25 surviving patients (48%) had stable disease; by EASL criteria, four patients showed complete response, four showed partial response, and four had stable disease. At 12 months of follow-up, one patient of the 12 with follow-up imaging (8%) had stable disease and the remaining 11 had progressive disease. Toxicities associated with the TACE procedures included upper abdominal pain (severe in 32% of patients, moderate in 40% and mild in 28%) and nausea (ECOG 3 in 12%, ECOG 2 in 43% and ECOG 1 in 45%).

Similar studies have been conducted with DC Bead®. Aliberti et al. performed an initial cohort study in 10 patients with liver-dominant mCRC refractory to systemic chemotherapy who underwent TACE with irinotecan-loaded DC Bead (Aliberti 2006). At one month of follow-up, all patients demonstrated significant reduction in tumor contrast enhancement and carcinoembryonic antigen (CEA) reduction of at least 50%. Objective tumor regression was observed in seven patients. The same research group published serial expansions of their cohort, eventually enrolling 82 patients (Fiorentini 2007, Aliberti 2011). Patients underwent one to four TACE cycles, and all showed reduction in metastatic contrast enhancement. At 3 months of follow-up 78% of patients demonstrated response by RECIST criteria, with a median duration of response of six months. Median survival across the entire cohort was 24 months, with 8 months of progression-free survival.

A later phase III study randomized 74 patients with less than 50% hepatic parenchymal replacement and no extrahepatic spread to TACE with irinotecan-loaded DC Bead and systemic fluorouracil, leucovorin and

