5.3 Follow-Up Schedule

- Patients should return for follow-up 4-6 weeks (28-42 days) post the second TACE cycle, then every 12 weeks (\pm 2 weeks) thereafter. Follow up may be more frequent if medically indicated
- Additional TACE procedures can be performed for residual or new disease as needed at the discretion of the physician; however, liver enzymes should be at acceptable levels before performing additional TACE cycles
- The liver should remain the dominant site of metastases for additional TACE cycles to be performed
- Each follow-up visit will include, at a minimum:
 - CT or MRI of the liver (the method of follow-up imaging should be consistent with baseline imaging)
 - PET or similar imaging to assess presence and/or progression of extrahepatic disease
 - Objective tumor response rate as determined by mRECIST criteria
 - Hematology and serum chemistry assessments as at baseline
 - Review of adverse events, including unscheduled hospitalizations
 - Review of any additional treatments performed outside of this registry for metastatic disease

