2.6. STUDY PROCEDURE

Study subjects (once screened, enrolled, and consented) must undergo a complete baseline evaluation. The evaluation includes haematology and serum chemistry assessments and imaging (CT or contrast-enhanced MRI of the liver).

Subjects must have two TACE cycles. A TACE cycle is defined as one embolization for patients with unilobar disease or two embolizations for subjects with bilobar disease (one for each lobe of the liver). The second TACE cycle should be performed within 2-4 weeks after the first TACE cycle. Subsequent TACE cycles may be performed for residual or new disease as needed (at the investigators discretion), based on tumor response. See 'Schedule of Procedures' below for additional information.

Schedule of Procedures

	Screening ¹	TACE Procedure ²	Follow Up Visits ³	Survival Follow-up ⁴
Informed Consent	X			
Eligibility criteria assessment	X			
Demographics	X			
Medical History	X			
Tumor Evaluation / Imaging	X		X	
Hematology / Serum Chemistry	X			
Embolization procedures (TACE)		X		
Pharmacokinetic Sampling ⁵		X		
Additional cancer treatments			X	
Adverse Events		X	X	
Survival status				X

¹ Screening imaging must be within 4 weeks of first TACE cycle.

² First TACE cycle must be within 4 weeks of screening imaging. If the patient has bilobar disease, the embolization of the first lobe must be within 4 weeks of screening imaging and the second lobe must undergo embolization within 3 weeks (\pm 2 weeks) of the first lobe. A second TACE cycle is required for all patients 2-4 weeks after the first TACE cycle. Additional TACE cycles can be performed for residual or new disease as needed.

³ Follow up Visits will start 4-6 weeks after the second TACE cycle and occur every 12 weeks (\pm 2 weeks) thereafter during the first year of follow-up. Follow-up may be more frequent if medically indicated.

⁴ If patients are no longer indicated for TACE, they will continue to be followed for survival for 2 years after the first TACE procedure, with contacts performed every 3 months (\pm 2 weeks).

⁵ Blood samples will be drawn for PK analysis from a portion of study patients after the first TACE procedure at the following time points; 30 min, 1 hour, 4 hours, 12 hours, and 24 hours or prior to discharge (whichever comes first).

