4. OUTCOME VARIABLES

4.1. PRIMARY OUTCOME

Patient survival will be calculated in months from the date of the first TACE procedure until a date of death is obtained or the subject is lost to follow up (utilizing the last successful contact with the patient). Median overall survival time will be the primary outcome of the study.

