4.3. OTHER PARAMETERS

Pharmacokinetic (PK) Analyses

PK blood samples drawn from a portion of the subjects after the first TACE cycle (at four pre-determined time periods) will undergo bioanalytical analysis using validated assays. The assays will measure the subject's plasma concentrations of irinotecan and its active metabolite, SN38.

Additional TACE Cycles

Overall survival time will be compared between standard TACE cycles and additional TACE cycles (any TACE procedure(s) beyond the protocol specified number of TACE cycles).

RECIST 1.1

Clinical outcomes will be re-analyzed based on RECIST 1.1 criteria. The best tumor response will be compared between mRECIST and RECIST 1.1.

Clinical Success

Similar to ORR, clinical success will be based on the last post-TACE liver response evaluated through mRECIST and RECIST 1.1 criteria. Clinical success is defined as the total number of confirmed subjects who exhibit a CR or PR [clinical success = (# CR + #PR)].

Demography and Baseline

Subject demographic information and other baseline data will be included and summarized. Sex, age, race, and ethnicity will be included as demographic characteristics. Medical history will be described through system organ class (SOC) and baseline risk factors. Subject hepatic health status such as prior hepatic treatment and tumor location will also be provided.

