5. STATISTICAL METHODOLOGY

5.1. GENERAL METHODOLOGY

Analysis will be performed when all subjects enrolled have been followed for survival for two years (24 months) from the date of their first TACE, are considered lost to follow up, or have died, whichever comes first.

For continuous variables, outputs will be presented with mean, standard deviation (SD), median, minimum, and maximum values. Mean and median will be rounded to a single decimal while SD will be rounded to two decimals. When appropriate, a corresponding 95% confidence interval (CI) will be calculated. Categorical variables (e.g., sex and race) will be reported using frequencies and percentages. All percentages will be rounded to single decimal. If percentages do not add up to 100% due to rounding, a footnote mention will be provided accordingly.

Correlation analyses will be used to analyze relationships for continuous variables. Fisher's exact test will be used to analyze relationships between categorical variables. P-values less than or equal to 0.05 will be considered significant. All p-values will be rounded to 3 decimal places and will be presented as "<0.001" if less than 0.0005.

Survival analyses will be performed using Kaplan-Meier with corresponding median survival times and 95% CIs.

Descriptive statistics will be used to examine demographic and baseline characteristics and to perform other efficacy analyses.

Each table generated will have headers that include the total sample size (N). Frequencies and percentages for categorical variables will be calculated using the number of subjects (n) with non-missing values.

DATA SOURCE

All data will be extracted from Medidata. Datasets will be merged and cleaned prior to data analysis. Data processing procedures will be documented to ensure replicability and error checking.

REPORTING OUTPUTS

SAS 9.4® and SPSS 27.0® will be used to produce all statistical analysis and figure outputs. Tables will be formatted through Microsoft® Word.

HANDLING OF MISSING DATA

There will be no imputation of missing data as the study is observational and all analyses performed should not require such methods.

SITE POOLING

To assess the consistency of observed treatment effect across investigational sites, a data poolability analysis will be performed on the primary efficacy outcomes of overall survival. Median overall survival data will be summarized by site, including Kaplan-Meier plots.

CLASSIFICATION OF PROTOCOL VIOLATION

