5.4. EXPLORATORY DATA ANALYSES

Pharmacokinetic (PK) Analyses

Data will be summarized by descriptive statistics, including mean, standard deviation, coefficient of variation, minimum, maximum, and median. The correlation between circulating levels of irinotecan and SN38 and overall survival, tumor response, and treatment-related adverse events will be evaluated to the extent possible with the available PK data. A Pearson's correlation or a Spearman's rank correlation will be performed depending on whether the variable being compared to levels of irinotecan and SN38 is continuous or categorical.

Additional TACE Cycles

Kaplan-Meier estimator with log-rank testing will be used to compare overall survival of standard TACE cycles to additional TACE cycles. Comparison of additional TACE cycles between tumor response will be performed using Fisher's exact test.

RECIST 1.1

The best tumor response will be compared between mRECIST and RECIST 1.1 using Fisher's exact test.

Clinical Success

Clinical success will be summarized using descriptive statistics.

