6.2. EXAMPLES

Table 1. Demographics and Baseline Characteristics

Characteristic	N = 105 n (%)	Mean	SD	Median	Min	Max
Age (Years)		xx.x	xx.xx	xx.x	xx	xx
Sex						
Male	xx (xx.x)					
Female	xx (xx.x)					
Prior Chemotherapy Treatment						
Yes	xx (xx.x)					
No	xx (xx.x)					
Baseline Disease Status						
Tumor Location						
Bilobar	xx (xx.x)					
Unilobar	xx (xx.x)					
Who Performance Status						
0 - Fully active, able to carry on all pre-disease performance without restriction	xx (xx.x)					
1 - Restricted in physically strenuous activity but ambulatory and able to carry out work	xx (xx.x)					
2 - Ambulatory and capable of all selfcare but unable to carry out any work activities	xx (xx.x)					

Table 2. Prior Chemotherapy History

Characteristic	N=101 n (%)	Total	Mean	Median	Minimum	Maximum
Previous Chemotherapy Cycles		xx	xx.x	xx.x	xx	xx
Previous Chemotherapy Treatment						
5FU	xx (xx.x)	xx				
Oxaliplatin	xx (xx.x)	xx				
Capecitabine (Xeloda)	xx (xx.x)	xx				
Cetuximab	xx (xx.x)	xx				
Regorafenib	xx (xx.x)	xx				
Leucovorin	xx (xx.x)	xx				
Irinotecan	xx (xx.x)	xx				
Bevacizumab (Avastin)	xx (xx.x)	xx				
Other	xx (xx.x)	xx				

Table 3. Safety Summary

Summary Variables	N=105 n (%)
Number of Adverse Events (AEs)	xx
Number of Subjects with at Least One AE	xx (xx.x)
Number of Serious Adverse Events (SAE)	xx
Number of Subjects with at Least One SAE	xx (xx.x)
Number of Adverse Events by Severity Level (N= xx*)	
Grade 1 (Mild)	xx (xx.x)
Grade 2 (Moderate)	xx (xx.x)
Grade 3 (Severe)	xx (xx.x)
Grade 4 (Life Threatening)	xx (xx.x)
Grade 5 (Fatal)	xx (xx.x)
Number of TACE-Related AEs	xx
Number of Subjects with at Least One TACE-related AE	xx (xx.x)
Number of TACE-Related AEs Leading to Death	xx
Number of Subjects with at Least One TACE-related AE Leading to Death	xx (xx)

*Denominator used for percentage calculations

Table 4. Median Survival (Overall and Liver PFS) and TTP

Outcomes	Median (in months)	Survival Rate	95 % CI
Overall Survival	xx.x		xx.xx – xx.xx
1-Year Survival		xx.x%	xx.xx – xx.xx
2-Year Survival		xx.x%	xx.xx – xx.xx
Liver PFS	xx.x		xx.xx – xx.xx
TTP			
Hepatic	xx.x		xx.xx – xx.xx
Extrahepatic	xx.x		xx.xx – xx.xx

Table 5. ORR and Clinical Success

Outcomes	mRECIST (N = 83)	RECIST 1.1 (N= 78)
CR: n	xx	xx
PR: n	xx	xx
Clinical Success*	xx	xx
ORR** (95% CI)	xx.x% (xx.x – xx.x)	xx.x% (xx.x – xx.x)

*Calculated as CR + PR

**Calculated as CR + PR / N

Table 6. Best Tumor Response

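### The survival comparison of standard with additional TACE cycles is an unadjusted log-rank test between selected groups, so differences in baseline prognosis can give a significant result in either direction with no treatment effect

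*SAP*

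**What the plan says.** SAP 5.4 plans the comparison as follows: "Kaplan-Meier estimator with log-rank testing will be used to compare overall survival of standard TACE cycles to additional TACE cycles". SAP 4.3 defines the second group by treatment received: "additional TACE cycles (any TACE procedure(s) beyond the protocol specified number of TACE cycles". The example Table 7 in SAP 6.2 splits the whole cohort into 76 standard and 29 additional patients and reserves a cell for the log-rank p-value. SAP 6.1 lists a Kaplan-Meier figure for the same contrast. SAP 5.1 sets the threshold: "P-values less than or equal to 0.05 will be considered significant".

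SAP 2.6 says who receives more cycles: "Subsequent TACE cycles may be performed for residual or new disease as needed (at the investigators discretion), based on tumor response". Protocol 5.3 asks for acceptable liver enzymes and adds: "The liver should remain the dominant site of metastases for additional TACE cycles to be performed".

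The baseline display, "Table 1. Demographics and Baseline Characteristics", has one column for all 105 patients. It includes tumor location and WHO performance status, but not by group. Neither SAP 5.4 nor any other section of the SAP names an adjustment, stratification or landmark for this comparison.

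**The concern.** The two groups are formed by a clinical decision, and the factors behind that decision are plausibly related to survival. A log-rank test treats the groups as if they differed only by chance and by the extra cycles. If patients with less liver disease or better general condition at entry are more likely to go on to further cycles, their better outlook is credited to the cycles. If further cycles go mainly to patients with persisting or new disease, the error runs the other way.

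Because Table 1 is not split by group, a reader could not see an imbalance. What is at stake is a p-value in Table 7 and a survival figure that may be read as evidence for or against giving more TACE.

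**Working it through.** The plan gives no power, event count or effect size for this comparison, so there is no stated figure to reproduce. Group sizes agree with enrolment: 76 + 29 = 105 = 100 + 5 (SAP 2.1).

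**Inputs from the documents.** Group sizes 76 and 29; threshold 0.05 (two-sided assumed); minimum follow-up 24 months. Prognostic spread comes from the case series in Protocol 1.0: "Median survival and time to progression were 21 months and 10 months among patients with less than 25% liver volume involvement", against a median survival of 7 months at 26-50% involvement. Both ranges fall within the entry limit of 50% of liver volume.

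**Assumptions.** Exponential survival, censoring uniform over 24-48 months, no effect of additional cycles, no immortal time, and the share of each group with 26-50% involvement.

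**Step 1: size of the spurious effect.** With exponential survival the hazard is ln 2 / median, so the high-involvement hazard is 21/7 = 3 times the low one. In units of the low hazard, a group with high-involvement share p starts at 3p + (1 - p). For 50% in standard and 25% in additional, this gives 2.0 and 1.5, a ratio of 0.75. It drifts towards 1 as high-risk patients die, and the simulated average is 0.78. The mixture medians solve p·2^(-t/7) + (1 - p)·2^(-t/21) = 0.5, giving 11.6 months (p = 0.50) and 15.7 months (p = 0.25).

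**Step 2: false-positive rate of the planned log-rank test.** Ranges come from repeated simulations of 2,000 and 4,000 trials per scenario.

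| High-involvement share, standard v additional | Hazard ratio at time zero | Simulated average HR | p ≤ 0.05 with no effect |
|---|---|---|---|
| 50% v 35% | 1.7/2.0 = 0.85 | 0.87 | 8-9% |
| 50% v 25% | 1.5/2.0 = 0.75 | 0.78 | 16-17% |
| 60% v 30% | 1.6/2.2 = 0.73 | 0.74 | 21-22% |

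Stratifying or adjusting for involvement returns 4-6%.

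Hand check of the middle row: expected deaths at an average follow-up of 36 months are 45.25 × (1 - 2^(-36/7)) + 59.75 × (1 - 2^(-36/21)) ≈ 85.5. Then z = √(85.5 × 76 × 29 / 105²) × |ln 0.78| ≈ 1.03, and Φ(1.03 - 1.96) ≈ 0.18, close to the simulated rate.

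**Step 3: sensitivity.** With shares reversed (35% in standard, 50% in additional), 11-12% are significant, now mostly against additional cycles. With strata of 18 v 12 months and shares of 50% v 25%, the rate is 7%. A separate simulation selected patients through an odds ratio between good prognosis and receipt, with half the patients in each stratum and censoring at 24 months. It gave 7%, 11%, 21% and 28% for odds ratios of 1.5, 2, 3 and 4, and 5.6-6.4% with the 18 v 12 month strata.

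**Step 4: does baseline adjustment alone repair the test?** SAP 4.1 starts the clock for everyone at the same point: "Patient survival will be calculated in months from the date of the first TACE procedure". The additional label is earned later. The second cycle falls 2-4 weeks after the first and the first follow-up visit 4-6 weeks after that, so response-guided cycles begin about 6-10 weeks after time zero or later. In the next simulation both mechanisms act: 21 v 7 month strata, odds ratio 2, no treatment effect, and assumed timing of the additional cycle.

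| Analysis | Cycle at 2-5 months | Cycle at 2-8 months |
|---|---|---|
| Unadjusted log-rank | 58% | 79% |
| Stratified by baseline factor, fixed label | 25% | 43% |
| Time-dependent exposure only | 11% | 10% |
| Time-dependent and stratified | 6.5% | 4.6% |

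An 8-month landmark with stratification gives 4.9% in the last column. Each correction alone leaves excess error; together they bring it to about the nominal level.

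**The case against.** Four points can fairly be made against this.

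First, the liver-dominance condition applies during follow-up, is worded as a recommendation, and leaves the choice to the physician. Liver dominance at baseline is an entry criterion for everyone. A reader might infer that the protocol sends better-prognosis patients to additional cycles by rule. The documents do not support that: no passage makes baseline liver involvement a criterion for further cycles, and the link to baseline prognosis is indirect. This stands, and it limits the claim to what an imbalance could do.

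Second, cycles given for residual or new disease could select patients with a worse outlook. A reader might infer that the bias must favour additional TACE; for baseline confounding that does not follow. This also stands, but a test that can err in either direction still needs adjustment.

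Third, the sizes rest on assumed shares and on subgroups of one 29-patient series. Shares of 50% v 25% and 60% v 30% imply odds ratios of 3 and 3.5; the milder 50% v 35% implies about 1.9 and gives 8-9%. This stands, so the sizes are illustrations, not estimates for this trial.

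Fourth, the analysis is exploratory, Protocol 2.3 makes it conditional on sufficient data and calls it a relationship, and no primary or secondary endpoint depends on it. That limits the importance of the point. It does not make the planned p-value valid.

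**Conclusion.** The concern holds in a limited form. The planned log-rank test compares selected groups without adjustment, and a baseline imbalance can make it significant in either direction when additional cycles do nothing. The false-positive rate is about 8-22% if the share with 26-50% involvement differs by 15-30 percentage points, and about 5-7% if the strata are closer to 18 v 12 months. These figures assume the protocol's 21 and 7 month medians (except where weaker strata are stated), the shares shown, and no immortal time. The trial's actual imbalance is unknown.

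A reader might also infer that a baseline-adjusted Cox model would restore the 5% level. It does so only when immortal time is excluded. Under the assumed timings, 25-43% false positives remain with a fixed label.

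Nor can it be taken that every covariate is to hand. WHO status and tumor location are in Table 1, and baseline extrahepatic imaging is in Protocol 5.1. Graded liver involvement is not in Protocol 5.1, SAP 4.3 or Table 1; eligibility needs only a check against 50%.

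**What to change.** In SAP 5.4, base inference on a hazard ratio with 95% CI from a Cox model instead of the log-rank p-value. Treat additional TACE as a time-dependent exposure, or fix a landmark in advance and classify patients who are alive and followed at that time. Adjust for baseline WHO performance status, tumor location (unilobar or bilobar) and extrahepatic disease, and for baseline liver involvement if the percentage is in the database. The sponsor should confirm that before writing it in. Add Standard and Additional columns to Table 1, and describe the result as an association in Table 7 and the figure.

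The cost is one extra model and a wider interval. With an assumed 60-90 deaths, an unadjusted fixed-group comparison already has SE(ln HR) = 1/√(deaths × 76 × 29 / 105²) = 0.29 to 0.24. The 95% limits therefore lie a factor of about 1.8 to 1.6 either side of the estimate, and the proposed model will be somewhat less precise. With WHO status as two terms, the full model has six parameters, or 10-15 deaths each.

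The change does not remove confounding by disease status after baseline. When extrahepatic progression was simulated to bar further cycles and raise the hazard two- to three-fold, time-dependent analysis still gave 7-10% false positives. The report should state this limit.

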2.3 Additional Analyses

If sufficient data is available, additional exploratory analyses will also be conducted. These may include, but are not limited to:

- Pharmacokinetic (PK) Analyses: Plasma concentrations of irinotecan and SN38 will be analyzed at the following timepoints after the first TACE procedure: 30 minutes, 1 hour, 4 hours, 12 hours, and 24 hours or prior to discharge (whichever comes first).
- Additional TACE Cycles: The relationship between 'Additional TACE cycles,' (defined as cycles a subject may undergo after the protocol specified TACE 1 and TACE 2) and overall survival time (in months)
- RECIST 1.1: Reanalyze clinical outcomes using RECIST 1.1 criteria and compare best tumor response between RECIST 1.1 and mRECIST criteria.
- Clinical Success: Similar to ORR, clinical success will be based on the last post TACE liver response evaluated through mRECIST and RECIST 1.1 criteria. Clinical success is the total amount of confirmed subjects that have a complete or partial response [clinical success = (# CR + #PR)]

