Outcomes	mRECIST (N =83) n (%)	RECIST 1.1 (N = 78) n (%)	p-value
Best Tumor Response	0.xxx		
CR	xx (xx.x)	xx (xx.x)	
PR	xx (xx.x)	xx (xx.x)	
SD	xx (xx.x)	xx (xx.x)	
PD	xx (xx.x)	xx (xx.x)	

Note: Percentages may not add up exactly due to rounding

Table 7. Additional TACE Cycles

Outcomes	Standard TACE Cycles (N=76)	Additional TACE Cycles (N=29)	Log rank test	Fisher's exact test
Median Overall Survival (in months)	xx.x	xx.x	p = 0.xxx	
Best Tumor Response: n (%)				p = 0.xxx
CR	xx (xx.x)	xx (xx.x)		
PR	xx (xx.x)	xx (xx.x)		
SD	xx (xx.x)	xx (xx.x)		
PD	xx (xx.x)	xx (xx.x)		
Not Assessed	xx (xx.x)	xx (xx.x)		

Note: Percentages may not add up exactly due to rounding

Table 8. PK Analyses

Variables	N	Mean	SD	Median	Min	Max	R (p-value)
Irinotecan (ng/ML): 30 minutes	xx	xxx.x	xxx.xx	xxx	xxx	xxx	
with Overall Survival							x.x (0.xxx)
with Tumor Response							x.x (0.xxx)
with Treatment-Related AEs							x.x (0.xxx)
Irinotecan (ng/ML): 1 hour	xx	xxx.x	xxx.xx	xxx	xxx	xxx	
with Overall Survival							x.x (0.xxx)
with Tumor Response							x.x (0.xxx)
with Treatment-Related AEs							x.x (0.xxx)
Irinotecan (ng/ML): 4 hours	xx	xxx.x	xxx.xx	xxx	xxx	xxx	
with Overall Survival							x.x (0.xxx)
with Tumor Response							x.x (0.xxx)
with Treatment-Related AEs							x.x (0.xxx)
Irinotecan (ng/ML): 24 hours	xx	xxx.x	xxx.xx	xxx	xxx	xxx	
with Overall Survival							x.x (0.xxx)
with Tumor Response							x.x (0.xxx)
with Treatment-Related AEs							x.x (0.xxx)
SN38 (ng/ML): 30 minutes	xx	xxx.x	xxx.xx	xxx	xxx	xxx	
with Overall Survival							x.x (0.xxx)
with Tumor Response							x.x (0.xxx)
with Treatment-Related AEs							x.x (0.xxx)
SN38 (ng/ML): 1 hour	xx	xxx.x	xxx.xx	xxx	xxx	xxx	
with Overall Survival							x.x (0.xxx)
with Tumor Response							x.x (0.xxx)
with Treatment-Related AEs							x.x (0.xxx)
SN38 (ng/ML): 4 hours	xx	xxx.x	xxx.xx	xxx	xxx	xxx	
with Overall Survival							x.x (0.xxx)
with Tumor Response							x.x (0.xxx)
with Treatment-Related AEs							x.x (0.xxx)
SN38 (ng/ML): 24 hours	xx	xxx.x	xxx.xx	xxx	xxx	xxx	
with Overall Survival							x.x (0.xxx)
with Tumor Response							x.x (0.xxx)
with Treatment-Related AEs							x.x (0.xxx)

[figure not shown]
[figure not shown]
[figure not shown]
[figure not shown]
Figure 1. Kaplan-Meier survival curve for overall survival**Figure 2. Kaplan-Meier survival curve for progression free survival**

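### Exploratory analysis only: Fisher's exact test, which assumes independent groups, is specified to compare mRECIST and RECIST 1.1 best response read on the same patients

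*SAP*

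**What the plan says.** SAP 5.4, under RECIST 1.1, states: "The best tumor response will be compared between mRECIST and RECIST 1.1 using Fisher's exact test". Protocol 7.3 names the same test. SAP 4.3 shows where the second set of results comes from: "Clinical outcomes will be re-analyzed based on RECIST 1.1 criteria". SAP 2.2 describes a single-arm study.

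The Table 6 shell in SAP 6.2 puts an mRECIST column (N=83) beside one headed "RECIST 1.1 (N = 78) n" and provides for one p-value. The choice follows the general rule in SAP 5.1 that Fisher's "exact test will be used to analyze relationships between categorical variables". The same section says how results will be read: "P-values less than or equal to 0.05 will be considered significant". No paired test, agreement measure or restriction to patients with both readings appears in either document.

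The comparison is exploratory and conditional. Protocol 2.3 says: "If sufficient data is available, additional exploratory analyses will also be conducted".

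A smaller, separate point concerns the PK analysis in SAP 5.4: "A Pearson's correlation or a Spearman's rank correlation will be performed depending on whether the variable being compared" is continuous or categorical. Table 8 has rows labelled "with Overall Survival" that report R with a p-value.

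**The concern.** Fisher's exact test on a table of criterion by response category treats the columns as independent samples. Here most or all patients contribute to both. The information on whether the criteria differ lies in the patients whose category changes from one criterion to the other, and the column counts do not show it.

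Because SAP 5.1 sets 0.05 as the threshold without exempting exploratory tests, the Table 6 p-value will be read as the verdict on whether the criteria differ. If the readings agree well, as two readings of the same patients may be expected to, the test seldom rejects even when the difference is real. A non-significant result could then be taken as support for using the criteria interchangeably. Within-patient agreement, which would inform that question directly, is not reported.

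**Working it through.** The plan gives no effect size, power or sample size for this comparison, so there is no figure to reproduce.

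**Overlap of the columns.** Inputs: 83 and 78 (Table 6) and 105 treated (Table 1 shell). Minimum in both columns: 83 + 78 − 105 = 56. Maximum: min(83, 78) = 78. The columns cannot be independent.

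**Could Fisher be meant for the 4×4 cross-tabulation?** That would test whether the readings are unrelated, which is a different question. Take a responder cross-table of 28 both, 5 mRECIST only, 5 RECIST 1.1 only and 40 neither. Each criterion finds 33 of 78 responders, so there is no difference. Fisher on that cross-table gives p<0.001; exact McNemar gives 1.0.

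**Same column counts, different pairing.** Assume 78 patients with both readings and CR+PR in 33 (mRECIST) against 22 (RECIST 1.1). Let b be responders on mRECIST only and c responders on RECIST 1.1 only, so b − c = 11. Fisher uses 33/78 against 22/78 and gives p=0.093 in every row. Exact McNemar is a two-sided binomial test of b out of b + c at one half. The paired difference is 11/78 = 14.1 points, with Wald standard error √(b + c − (b − c)²/78)/78.

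| b, c | kappa | Fisher p | McNemar p | 95% CI for difference (points) |
|---|---|---|---|---|
| 11, 0 | 0.70 | 0.093 | 0.001 | 6.4 to 21.8 |
| 13, 2 | 0.59 | 0.093 | 0.007 | 4.9 to 23.3 |
| 16, 5 | 0.42 | 0.093 | 0.027 | 3.0 to 25.2 |
| 19, 8 | 0.26 | 0.093 | 0.052 | 1.4 to 26.8 |
| 23, 12 | 0.04 | 0.093 | 0.090 | −0.4 to 28.6 |

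**Rejection rates.** These come from exact enumeration of the multinomial for 78 pairs at two-sided 0.05. True CR+PR rates are assumed. Agreement falls from left to right as changes in the reverse direction (c) become more common.

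| True CR+PR | kappa | Fisher | McNemar |
|---|---|---|---|
| 42% vs 32% | 0.79 / 0.70 / 0.58 / 0.36 / 0 | 4 / 7 / 10 / 15 / 21% | 80 / 59 / 42 / 29 / 20% |
| 42% vs 27% | 0.68 / 0.59 / 0.46 / 0.24 / 0 | 39 / 41 / 42 / 44 / 45% | 98 / 87 / 72 / 54 / 43% |
| 42% vs 22% | 0.56 / 0.34 / 0 | 83 / 77 / 72% | 99.9 / 90 / 71% |
| 42% vs 42% (no difference) | 0.79 / 0.59 / 0 | 0.0 / 0.1 / 3.4% | 1.8 / 2.8 / 3.4% |

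**Four categories in the 83 and 78 layout.** This is a simulation of 500 replicates (standard error about 2 points). The assumed CR/PR/SD/PD mixes are 12/30/33/25% for mRECIST and 7/20/46/27% for RECIST 1.1, with latent correlations of 0.5, 0.7 and 0.9. With 78 patients in both columns, Fisher rejects in 35/34/20% and Stuart-Maxwell in 48/67/87%. With 56 in both, the figures are 38/33/29% and 35/43/76%.

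**PK note.** Overall survival in months is continuous, so SAP 5.4 appears to send it to Pearson correlation. Under SAP 4.1, a patient lost to follow-up contributes time to last contact, and R would treat that as a survival time. Assuming exponential survival, a hazard ratio of 1.65 per SD of PK level and medians of 10 to 24 months, R is −0.31 to −0.40, against −0.40 with complete follow-up. At a 7-month median it is not attenuated.

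**The case against.** The strongest reply is that little depends on this. One p-value in one conditional, exploratory table is affected, and no primary or secondary result uses it. The error is also in the safe direction: in the no-difference scenarios with two categories Fisher rejects in at most 3.4%, so the nominal 5% is kept. A large difference would usually still be found: at 42% against 22%, Fisher has 72–83% power. All of this stands and limits the weight of the point. It does not make the test suitable, because a procedure that rejects in about 0% of null cases at high agreement loses most of its power against moderate differences.

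A second reply is that an overlap of 56 is unlikely. SAP 4.2 calculates ORR for the efficacy population and Table 5 gives its mRECIST N as 83, so the 78 probably lie within the 83. That is the more natural reading, but neither document states it. The figure of 56 is only a bound. At that bound with low agreement the paired test gains no power, and the argument is then about validity alone.

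Third, the agreement and response rates are assumed. They are, and the range includes the point where the advantage disappears.

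Finally, the PK point is a different error in a different table, its effect is modest, and PK is sampled in only a portion of patients. It is kept here as a side note, and the main point does not depend on it.

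**Conclusion.** The concern holds. The plan assigns an independent-groups test to paired readings, in both documents, and no other text corrects it. With positive agreement the resulting p-value is too conservative, and more so as agreement rises. At 78 pairs and an assumed 42% against 32%, Fisher's power is 4% against McNemar's 80% at kappa 0.79, and the two are about equal at kappa 0. These sizes rest on assumed response rates, agreement and overlap. That the test is wrong for these data does not.

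The reach is limited. Overall survival, ORR with its interval, and the Table 6 counts and percentages are unaffected. Table 7 also uses Fisher's test, but between different patients (76 and 29), and is not part of this point. The plan should be changed, as a correction to an exploratory analysis.

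**What to change.** In SAP 5.4, restrict the test to patients read under both criteria and state their number in Table 6. Add the 4×4 cross-tabulation. Name one test in advance. Exact McNemar on CR+PR is the simplest. If all four categories are to be tested, use Stuart-Maxwell for equal distributions or Bowker for symmetry (these are different hypotheses), with exact or Monte Carlo p-values if cells are sparse. Report the paired difference in CR+PR with its 95% CI, and weighted kappa. Patients read under one criterion only stay in the descriptive columns. If the overlap proves well below 78, a comparison of CR+PR clustered on patient (GEE with robust variance) keeps every reading. Protocol 7.3 names the same test, so the change should be recorded against it.

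The cost is SAP wording and one table shell. No new data are needed, and the procedures are standard in SAS 9.4. The paired test leaves out 5 of the 83 if all 78 are among them. At the minimum overlap it leaves out 83 − 56 = 27 and 78 − 56 = 22.

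Minor: in the overall survival rows of Table 8, replace R by a Cox hazard ratio per unit of log concentration with 95% CI, or state that R treats censored times as survival times.
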